6.3 Treatment Discontinuation

The end of treatment visit will occur at the C1 D28 visit in subjects with progressive disease or those in Phase Ib who develop DLT or at study withdrawal, even if the date does not correspond to a protocol-specified visits. Other reasons for withdrawal of treatment are given in [Section 4.2](#). For subjects completing study stipulated two cycles of treatment (phase II portion of the study) will complete end of treatment assessment as described in section 7.2

6.4 Follow up/Survival

Subjects will have a follow-up visit for the evaluation of adverse events and concomitant medications 28 days (± 7 days) after the last study medication dose.

Follow-up evaluations will be performed for clinically significant abnormal physical examinations or abnormal laboratory findings, 12-lead ECGs, or vital signs, as deemed necessary by the treating physician.. All subjects who have adverse events, whether considered associated

with the use of the study drugs or not, must be monitored to determine the outcome. The clinical course of the adverse event will be followed according to accepted standards of medical practice, even after the end of the period of observation, until a satisfactory explanation is found or the Principal Investigator deems it medically justifiable to terminate follow-up.

All subjects will be followed monthly until: disease progression, death, or until 3 years from the on-study date.

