Rationale:	There is a paucity of treatment options for subjects with resistant AML. Recently AML has been shown to be a multi-genetic disease with sub-clonal architecture that evolves spontaneously and in response to treatment. Chemotherapy-resistant leukemic clones can quickly gain dominance by “survival of the fittest” dynamics. One way of targeting minor yet resistant clones is to augment the effectiveness of current chemotherapy drugs. Hromas et al. discovered the importance of the Metnase complex in repairing chemotherapy related DNA damage in leukemia and other cancers (1-3). Screening studies identified ciprofloxacin as a Metnase inhibitor that chemosensitizes leukemic myeloblasts to etoposide chemotherapy (4). The non-overlapping toxicity profiles of ciprofloxacin and etoposide, and their additive effectiveness in this model, make these agents attractive candidates for use in combination in subjects with resistant AML.
Primary Objective:	
In subjects with resistant AML, to
 
 Phase 1b: Establish the maximum tolerated dose (MTD) of oral ciprofloxacin when given in combination with a fixed dose of oral etoposide to subjects with resistant AML. Phase II: Determine the complete response (CR, CRi, and CRp, see Appendix A) rate to treatment with ciprofloxacin and etoposide at the MTD in adults with resistant AML.
Secondary Objectives:	
In subjects with resistant AML, to
 
 Determine the safety and feasibility of treatment with oral ciprofloxacin and etoposide; Measure duration of complete response, of progression free survival and of overall survival following treatment with oral ciprofloxacin and etoposide; and Estimate the incidence of Grade ≥ 3 adverse events following treatment with ciprofloxacin and etoposide.
Study Design:	This is an open-label, single arm, Phase Ib/II study of oral ciprofloxacin and etoposide in subjects with resistant AML. This study is designed to evaluate the complete response rate, the safety profile, and biologic activity of the combination of oral ciprofloxacin and etoposide in subjects with resistant AML. For both study phases, all subjects will receive 1 cycle of induction. At the end of Cycle 1, subjects who demonstrate progressive disease will have completed study treatment. For any subject who demonstrates stable disease or a

partial response, a second cycle of induction will be given. No subject will receive more than 2 cycles of induction.

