Phase Ib:

In the **Phase Ib** portion of the study, subjects will be enrolled in cohorts of three (3) in a traditional 3+3 study design (5). The starting dose is level “0” and includes: ciprofloxacin 750 mg orally twice daily on Days 1 - 10 and etoposide 200 mg orally once daily on Days 2 – 8. During the first cycle of treatment, subjects will be individually assessed for safety and dose limiting toxicity (DLT) for the purpose of determining the MTD of ciprofloxacin. The MTD will be defined as the highest dose of ciprofloxacin at which < 33% of the subjects treated at a given dose level experience a DLT (See [Figure 1](#)). The **Phase Ib** portion of this study ends when a MTD is identified among the three planned dose levels (See [Table 2](#)).

Subjects withdrawn before Cycle 1 Day 1 (C1D1) will not be evaluable for dose escalation decisions and will be replaced in their treatment cohort. A subject is evaluable for dose-escalation decisions provided: they receive all drug doses and remain on study until evaluation at Cycle 1 Day 28 without a DLT; or they experience a DLT during Cycle 1. Subjects who miss any etoposide or ciprofloxacin doses or withdraw from study without a DLT and prior to Cycle 1 Day 28 are not evaluable for dose escalation decisions and will be replaced in their cohort of treatment.

During dose escalation no more than 3 subjects will be treated simultaneously at any given dose level. The **Phase Ib** portion of this study will not be complete until > 28 days after accrual of the last subject.

Phase II:

Enrollment in the **Phase II** portion of the study will begin once the MTD has been determined. After Cycle 1, subjects with progressive disease will be removed from the study. Other study participants will continue to receive a second 28-day cycle of ciprofloxacin and etoposide at the MTD or until one of the following occurs: disease progression, unacceptable toxicity, consent withdrawal, completion of Cycle 2, or termination of the study.

Dose Limiting Toxicity (DLT)

DLT will be defined as any of the following events that are considered to be related to treatment with ciprofloxacin and etoposide. For the purpose of dose-escalation and MTD determination, only DLTs that occur during the first cycle of oral ciprofloxacin and etoposide will be considered. These include:

1. Any Grade \geq 3 non-hematologic toxicity, except alopecia; and vomiting or nausea uncontrolled by medical management;

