	
I. Males with female partners of child-bearing potential must agree to use physician-approved contraceptive methods (e.g., abstinence, condoms, vasectomy) throughout the study and should avoid conceiving children for 6 months following the last dose of ciprofloxacin and/or etoposide.
 
J. Subjects must have provided written informed consent, and demonstrated the willingness and ability to comply with all study-related procedures.
 
Exclusion criteria - None of the following can apply:
 
A. History of allergic or significant adverse reaction (e.g., anaphylaxis, prolonged QTc, or severe tendonitis) to ciprofloxacin or etoposide.
 
B. Acute promyelocytic leukemia (APL) with t(15;17).
 
C. Prolonged baseline QTc, defined as QTc interval > 470 msec in women and > 450 msec in men, or > 480 msec for subjects with a bundle branch block.
 
D. Uncontrolled clinically significant infection. Subjects with fever (temperature $\geq 38.3^{\circ}\text{C}$) thought to be related to leukemia are eligible assuming that blood cultures are negative during the 7 days prior to Cycle 1 Day 1 and there is no clinical evidence of active infection (e.g., negative or stable radiographs and negative physical examination).
 
E. Ongoing, symptomatic Clostridium difficile infection. Subjects who are asymptomatic with negative stool for C. difficile may participate.
 
F. Pregnant and/or nursing.
 
G. History of Myasthenia Gravis.
 
H. Treatment with any anticancer therapy (standard or investigational) within 14 days prior to the first dose of ciprofloxacin or less than full recovery (\leq CTCAE Grade 1) from the clinically significant toxic effects of that treatment. The use of hydroxyurea is allowed only during the first 14 days of cycle 1.

Study Duration and Dates:
	
 • It is estimated that the subject recruitment period will be approximately 48 months. No subject will receive more than 2 cycles of therapy from Day 1 of Cycle 1. • Data regarding disease status and overall survival will be collected monthly until disease progression, death or until 3 years from the on-study date.

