Safety Assessments:	
Subjects will be evaluated weekly during and for at least 28 days following the last cycle of chemotherapy. Assessments will include (See Table 1):
 
 • Interval history, review of systems, medications, new allergies, and physical examination with vital sign measurements; • Weekly laboratory assessments, including a CBC with differential and CMP; and • Toxicity assessment per the NIH Common Toxicity Criteria Adverse Event (CTCAE) version 4.
Efficacy Assessments:	
Efficacy parameters used to assess response include hemoglobin, ANC, platelet count, circulating blasts, and bone marrow aspirate and/or biopsy.

Sample Size Estimation	
In prior clinical trials of oral etoposide in resistant AML the CR rate has been approximately 20%. It is expect that the combination of etoposide with ciprofloxacin will improve CR to 40%. In order to detect this difference with type I error rate of 0.10 and power of 80%, when the true response rate is 40%, a minimum of 24 evaluable subjects will be treated in Phase II based on the Simon’s two-stage MiniMax design. Accounting for 15-20% drop out rate, a total of 30 subjects will need to be recruited to this phase.

Table 1. Study Events Schedule

Assessment	Screen (≤ 21 days prior to Day 1)	Cycle 1					Cycle 2		End of Treat- ment ¹² ± 7days	Long- Term Follow Up ¹³
		Day 1	Day 8±2	Day 15±2	Day 22±2	Day 28±2	Days 1, 8, 15, 22±2	Day 28±2		
Signed Informed Consent	X									
Demographics	X									
Medical /Treatment History	X									
Medication History ¹	X	X	X	X	X	X	X	X	X	
Interval History/Physical Examination	X	X	X	X	X	X	X	X	X	
Toxicity Assessment		X	X	X	X	X	X	X	X	
Review of Systems		X	X	X	X	X	X	X	X	
Weight	X	X	X	X	X	X	X	X	X	
ECOG Performance Status	X	X	X	X	X	X	X	X	X	
12-lead electrocardiogram (ECG) ²	X		X			X			X	
Vital Signs ³	X	X	X	X	X	X	X	X	X	
Hematology Laboratory Evaluations ⁴	X	X	X	X	X	X	X	X	X	
Blood Chemistry Laboratory Evaluations ⁵	X	X	X	X	X	X	X	X	X	
Serum Pregnancy Test (females) ⁶	X					X		X	X	
Administer Ciprofloxacin ⁷		X	X				X			
Administer Etoposide ⁸			X				X			
Bone Marrow Aspirate and/or Biopsy ⁹	X					X		X	X	
Adverse Events Assessments ¹¹	X	X	X	X	X	X ¹³	X	X	X	
Survival Assessment										X

¹ Document all medications taken during the two (2) weeks prior to screening and throughout and for 28 days after last treatment.

² Includes: rhythm, rate, and PR, QRS, and QTc intervals.

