2.2 Secondary

In subjects with resistant AML, to

- Determine the safety and feasibility of treatment with ciprofloxacin and etoposide;
- Measure the response duration, progression-free and overall survival (PFS and OS respectively);
- Estimate the incidence of Grade ≥ 3 adverse events following treatment with ciprofloxacin and etoposide at the MTD.

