No more than 3 subjects will be added simultaneously to a dose cohort during dose escalation. The Phase Ib portion of this study ends when the MTD has been identified.

Subjects entered during Phase 1b who develop DLT with the first cycle will be withdrawn from the study. Subjects who do not develop DLT with the first cycle, will be treated in a second repeated 28-day cycle with ciprofloxacin and etoposide at the dose level given during Cycle 1

until completion of Cycle 2, disease progression, unacceptable toxicity, consent withdrawal, PI decision to discontinue treatment, or termination of the study. Intra-subject dose escalation will not be permitted. No subject will receive more than 2 cycles of treatment.

Figure 1. Example of How MTD Will Be Determined in Cycle 1

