3.4 Phase II

Enrollment in the Phase II portion of the study (dose expansion) will begin once the MTD has been determined. After Cycle 1, subjects with progressive disease will be removed from study. Others will continue to receive 28-day cycles of ciprofloxacin and etoposide at the same dose level until completion of Cycle 2, disease progression, unacceptable toxicity, consent

withdrawal, PI decision to discontinue treatment, or termination of the study. No subject will receive more than 2 cycles of therapy.

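### As written, survival follow-up stops at disease progression, so overall survival, a secondary objective, can be estimated only under a censoring assumption that the collected data cannot test

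*Combined protocol and SAP*

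**What the plan says.** OS is an objective in two places. The synopsis (Secondary Objectives) states: "Measure duration of complete response, of progression free survival and of overall survival following treatment with oral ciprofloxacin and etoposide". Section 2.2 states: "Measure the response duration, progression-free and overall survival (PFS and OS respectively".

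The end of follow-up is given in three places, each listing progression as a stop:

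- Section 6.4: "All subjects will be followed monthly until: disease progression, death, or until 3 years from the on-study date".
- Table 1, footnote 13: the same sentence. This footnote governs the Long-Term Follow Up column, which holds the table's only "Survival Assessment".
- Synopsis, Study Duration and Dates: "Data regarding disease status and overall survival will be collected monthly until disease progression, death or until 3 years from the on-study date".

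The synopsis (Phase II) adds: "After Cycle 1, subjects with progressive disease will be removed from the study". Section 3.4 says the same: "After Cycle 1, subjects with progressive disease will be removed from study". Section 3.3.1 covers another group: "Subjects entered during Phase 1b who develop DLT with the first cycle will be withdrawn from the study".

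Section 11.3.2 offers frequency distributions and 95% confidence intervals for proportions. It gives no definition of OS, no censoring rule and no time-to-event method.

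**The concern.** On the natural reading, monthly contact ends at the first of progression, death or 3 years. Deaths before progression are recorded; deaths after it mostly are not. An OS curve then has to censor subjects at progression, which is the event most likely to change their risk of death. Whatever survival is after progression, the recorded data look the same, so no later analysis can check or repair the assumption.

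What is at stake is a descriptive secondary estimate. The CR endpoint, the Simon rule and the sample size do not depend on it, and PFS is largely untouched because its events are collected.

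**Working it through.** **1. Is there another route to deaths after progression?** There are two, both partial.

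- *Safety window* (sections 6.4 and 8.2): 28 (±7) days after the last dose; section 9.1 says at least 28 days. The last ciprofloxacin dose in a cycle is on Day 10 (section 4.1), so the window closes on Day 10 + 28 = Day 38 (31 to 45). For progression found at the Day 28 (±2) visit, it adds 38 − 28 = 10 days (31 − 30 = 1 to 45 − 26 = 19). With the ±7-day marrow tolerance in section 7.2.1 it adds 0 to 24 days.
- *Adverse-event outcome monitoring* (sections 6.4 and 8.3): section 8.1.1 lets an adverse event include worsening of the disease under treatment, so some later deaths may be recorded. The investigator may end this monitoring. Under section 8.2, general adverse-event collection stops at new anti-cancer therapy, except for related or clinically significant events.

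**2. Size of the error (illustration).** The plan has no OS figure to reproduce, and all rates here are assumptions. Take constant hazards, median PFS 2 months, a share *p* of first events being progression, and median survival after progression *m*. With L = ln2/2 and M = ln2/m per month:

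- True OS: S(t) = exp(−Lt) + [pL/(L − M)]·[exp(−Mt) − exp(−Lt)]
- Kaplan-Meier limit when censored at progression: exp(−(1 − p)Lt), with median 2/(1 − p)

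| p | Median if censored at progression | True median, m = 3 | True median, m = 12 |
|---|---|---|---|
| 60% | 5 | 4.15 | 7.15 |
| 80% | 10 | 5.10 | 11.32 |
| 90% | 20 | 5.56 | 13.30 |

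Medians are in months. The two curves coincide when m = 2/(1 − p). At m = 3 the censored estimate is too long in all three rows. At m = 12 it is too short at 60% and 80%, and too long at 90%.

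At m = 3 the safety window would catch 1 − exp(−M × 10/30.44) = 7.3% of deaths after progression (0.8% to 13.4% for 1 to 19 days; 0 to 16.7% for 0 to 24 days). This is a floor, because adverse-event monitoring may add more.

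**3. Would a median be estimable?** The documents do not fix the OS population. The Simon evaluable count is 24. Enrolment is 8-24 in Phase Ib plus 30 (section 11.1) or up to 44 (section 3.1, Number of Subjects) in Phase II: 8 + 30 = 38, 24 + 30 = 54, 24 + 44 = 68. Simulated share of trials in which the Kaplan-Meier median is not reached:

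| n | p = 60% | 80% | 90% |
|---|---|---|---|
| 24 | 7% | 49% | 78% |
| 38 | 3% | 43% | 77% |
| 54 | 1% | 37% | 76% |
| 68 | 0.4% | 34% | 75% |

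With 54 subjects, expected deaths before progression are 54 × (1 − p) = 21.6, 10.8 and 5.4. If vital status were followed to 3 years with m = 3, almost all 54 deaths would be seen.

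**4. The same data fit different OS values.** Assume median time to progression 2 months (hazard a = ln2/2 = 0.347 per month) and a death hazard without progression of 0.03 per month. At 6 months the censored Kaplan-Meier estimate is exp(−0.03 × 6) = 84%. True OS is 34%, 53% or 63% for median survival after progression of 2, 4 or 6 months, with identical recorded data. Without any assumption, OS lies between PFS, exp(−0.377 × 6) = 10%, and PFS plus everyone who has progressed, 10% + (0.347/0.377) × 90% = 93%.

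**The case against.** **The text can be read another way.** The synopsis pairs disease status and survival with a list of stops and does not say that the first one applies. One could read it as disease status to progression and survival to death or 3 years. That reading gives the Long-Term Follow Up column a purpose for subjects who progress in Cycle 1. The Study Design text in the synopsis and section 3.1 (Overview) say only that such subjects have completed treatment, and the protocol uses withdrawal loosely. This reading is possible but stated nowhere, and none of these passages schedules a survival contact. If it is what the sponsor meant, a clarifying sentence is still needed.

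**The bias may be small.** With m = 3 and lower progression shares, the same formulas give 4.0 months censored against 3.7 true at 50%, 3.3 against 3.3 at 40%, and 2.9 against 2.9 at 30%. Lower shares are plausible: Appendix A defines progression only by marrow blasts, and section 6.2 leaves marrows after end of treatment to clinical indication. This stands as a limit on the size. It does not make the assumption testable.

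**OS is descriptive.** There is no OS hypothesis, comparator or decision rule, and section 7.1.2 names CR as the efficacy outcome. This also stands and limits the weight of the point. Bounds free of assumptions exist, but they are too wide to serve as an estimate.

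**Conclusion.** The concern holds and should be fixed. Followed as written, the plan loses most deaths after progression, so a declared secondary objective cannot be estimated without an assumption the data cannot test. This conclusion rests on the text. The size rests on assumed rates: the censored median can be far too long (20 against 5.6 months), about right, or too short (5 against 7.15 months). The primary endpoint, the Simon design and the sample size are not affected.

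**What to change.** - **Synopsis (Study Duration and Dates), Table 1 footnote 13 and section 6.4:** separate the two kinds of follow-up. Collect disease status until progression. Collect vital status monthly, by phone or chart, for every treated subject until death, withdrawal of consent or 3 years, regardless of progression, treatment discontinuation or new therapy.
- **Synopsis (Phase II), section 3.4, and the other places where subjects are withdrawn or removed (sections 3.3.1, 4.1, 4.2, 4.4 and 4.4.1.2):** state that leaving treatment does not end survival follow-up. No treatment-stopping rule changes.
- **Section 11.3.2:** define OS as the time from Cycle 1 Day 1 to death from any cause in all treated subjects, censored at the date last known alive, and estimate it by Kaplan-Meier with a 95% confidence interval. The on-study date, which the protocol uses for its 3-year limit, could serve as the time origin instead; the choice is minor but should be stated.

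**Cost:** a protocol amendment with IRB review, possibly a consent amendment, and a monthly phone or chart check for subjects who have progressed or left treatment. No visits or procedures are added. Data collection runs slightly longer, and OS will include the effect of later therapies.

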7. DATA MEASUREMENTS AND METHODS OF COLLECTION

7.1 Data Measurements

7.1.1 Safety Data

Safety variables for this study include the following:

- DLTs;
- Physical examinations;
- Vital signs;
- 12-lead ECGs;
- Clinical laboratory measurements, including hematology and serum chemistry; and
- Adverse events.

7.1.2 Efficacy Data

The efficacy outcomes of interest will be CR (including CRi and CRp) as defined in [Appendix A](#). The efficacy variables, which will be used to assess response, include hemoglobin, ANC, platelets, circulating blasts, bone marrow aspirate and biopsy.

7.2 Collection Methods

7.2.1 Bone Marrow Samples

Bone marrow aspiration and biopsy will be collected using standard institutional procedures at the following time points:

- Screening: within 42 days prior to Cycle 1 Day 1;
- Day 28 (± 7 days) after each cycle until CR or progressive disease

Bone marrow aspirations (6 to 8 mL) and core biopsies will be collected as per standard of care for leukemia treatment. As per standard of care, these specimens will also be sent for flow cytometry. Routine cytogenetics, FISH and genetic analysis will be obtained if abnormalities were present at the time of study entry.

7.2.2 Safety Measurements

Safety measurements for this study include AEs, clinical laboratory measurements (hematology and serum chemistry), physical examination findings, vital signs, and 12-lead ECGs.

7.2.3 Adverse Events

Adverse events that occur prior to dosing will be collected on Day 1 by questioning the subject regarding their occurrence since the screening visit. Adverse events will be collected at each

clinic visit based on observation and spontaneous reporting.

7.2.4 Clinical laboratory assessments

Clinical laboratory assessments are outlined in [Table 1](#).

Hematology assessments will be performed during the Screening period and on Days 1, 8, 15, 22, and 28 of each cycle. The hematology assessments will include:

- Complete blood count (CBC) including hemoglobin, hematocrit, white blood cell (WBC) absolute differential including circulating blasts, and platelet count.

Blood chemistry assessments will be performed during the Screening period on Days 1, 8, 15, 22, and 28 of each cycle. The chemistry assessments will include:

- Electrolytes: (sodium, potassium, calcium, magnesium, phosphorous, bicarbonate, and chloride);
- Renal function: (BUN, creatinine, and uric acid);
- Liver function: SGOT (also known as AST), SGPT (also known as ALT), total bilirubin;
- LDH, and alkaline phosphatase; and
- Other: (glucose, albumin, and total protein).

Serum pregnancy tests for females of childbearing potential will be performed during the screening period and on day 28 of each cycle. If delayed, a pregnancy test will be repeated within 7 days of the first day of the next cycle.

Approximately 50 mL of blood will be collected for safety assessments from each subject over the course of each 28-day cycle.

Abnormal, clinically significant results as assessed by the Principal Investigator should be repeated to rule out laboratory error. Persistent relevant abnormal changes from baseline must be followed up until the cause is determined or until they return to the premedication value. Hematology and serum chemistry will be carried out according to the standard operating procedures by the validated local laboratory.

